6.9 Prohibited Medications during the study therapy

[figure not shown]
The following treatments are not allowed at inclusion and during treatment period :

- For all patients :
 - Other investigational drugs;
 - Sorafenib;
- Only for patients randomised in the Doxorubicin Transdrug™ groups:
 - TACE;
 - Loco-regional treatment (Percutaneous ethanol...);
 - Cytotoxic drugs;
 - Interferon;
 - Recently introduced statins (less than 1 month);
 - Hormone therapy.

6.10 Post study therapy

No cross over to DT is allowed for the patients enrolled in the control arm. After disease progression, patients in both arms will be allowed to receive any anti cancer therapy as deemed appropriate by the investigator including Sorafenib. Post anticancer therapy will be recorded in the eCRF.

7 TRIAL PROCEDURES

7.1 Screening (Day-28 to Day-1)

Within 28 days (\pm 2 days) before baseline visit (D0 Cycle 1), all patients (DT groups and control group) will have the following investigations performed after collection of signed and dated Informed Consent form (ICF).

- Medical history and demographic data: including HCC history with staging information (Child-Pugh (appendix II), CLIP (appendix III), MELD (appendix III) and BCLC (appendix I)), prior treatments;
- Concomitant diseases and medications will be recorded;
- Physical examination: a full physical examination will be performed: height, body weight (BW) and ECOG performance status (appendix IV) will be recorded;
- Vitals signs: subject's vital signs will be recorded after a rest of at least 5 minutes: Blood pressure (BP), Heart rate (HR), Respiratory rate (RR), Oxygen saturation (SaO₂), body temperature in °C;
- ECG recording: print-outs for each ECG will include: date, time, initials of the investigator or its deputy, at least 2 complexes for each lead and v₅ for monitoring HR and cardiac conduct changes. The corresponding source data will consist on the cardiograph paper print-outs;

- Left ventricular ejection fraction (LVEF) evaluation using cardiac ultrasound or cardiac scintigraphy; the same technique for the same patient is recommended throughout the study;
- Respiratory Function Tests: vital capacity (VC), total lung capacity, carbon monoxide diffusing capacity (DLCO), Forced Expiratory Volume in one second (FEV₁);
- Clinical laboratory tests:
 - Haematology: complete blood counts (CBC), platelets count;
 - Biochemistry: AST, ALT, GGT, ALP, total bilirubin, albumin, protein electrophoresis, ferritin, CRP, LDH, CPK;
 - Na⁺, Cl⁻, K⁺, HCO₃⁻, urea and creatinine;
 - Coagulation: INR/Prothrombin, Factor V;
 - Calcium and phosphorus;
 - Metabolism : Total cholesterol, triglycerides, glycaemia;
 - α-foetoprotein (AFP);
 - Serum β-HCG for women of childbearing potential.

Factor V and protein electrophoresis (at screening, baseline and throughout the study) are not mandatory if sites cannot perform these tests at their routine local lab. For Egyptian sites, a central lab may be used.

- Imaging:
 - Chest X-ray;
 - Abdominal and pelvic including hepatic spiral CT scan or MRI;
 - Thoracic CT scan.

[figure not shown]
If one of these imaging have been realized as part as routine pratice before screening (i.e. before ICF signed), these radiologic exams can be considered as sufficient for the screening period if realized within 28 days before baseline.

[figure not shown]
7.2 Trial Period

7.2.1. Design of each Cycle of treatment during treatment period

[REDACTED]

7.2.1.1 On Day 0 (24h before study treatment)

- | [Redacted]

7.2.1.2 On Day 1 – Treatment visit

[Redacted]

[Redacted]

- [Redacted]

- | [Redacted]

- [Redacted]

- [Redacted]

- | [Redacted]

- [Redacted]
- [Redacted]
- [Redacted]

- | [Redacted]

- | [Redacted]

- | [Redacted]

- | [Redacted]

- [Redacted]

- | [Redacted]

- | [Redacted]

[Redacted]

[Redacted]

➤

[Redacted]

[Redacted]

7.2.1.3 On Day 2 and Day 3 (optional) after study treatment

[Redacted]

[Redacted]

[Redacted]

[Redacted]

[figure not shown]
7.2.1.4 On Day 14 after study treatment

[Redacted]

[figure not shown]
[Redacted]

[Redacted]

[figure not shown]
7.2.2 Additional Cycles.

[figure not shown]
[figure not shown]

7.2.3 End of treatment Notification

[figure not shown]

7.2.4 End of Study treatment visit: 1 month after last infusion

7.2.5 Follow-up period

7.3 Biobank and biological material taken during the study

During the study, biological material consisting of blood samples will be taken and stored. The biological material will be kept in a biobank, initially stored in trial centres and later on sent to Onxeo (formerly known as BioAlliance Pharma) and to Pharmacokinetics department – Bertin Pharma at CEA/LEMM (France). All biological material will be anonymised and the sponsor will not be aware of the participants' identities. All samples will be kept in the biobank for 15 years maximum after the end of the study, and will then be destroyed. The biological material can only be used in a new research project after acceptance from legal authorities.

7.3.1. Pharmacokinetic study

The pharmacokinetic study of DT will be performed only in selected centers that can meet the requirements of blood sampling.

The primary aim of pharmacokinetic evaluation will be to determine the population pharmacokinetic parameters. The secondary objective will be to analyse the pharmacokinetic/pharmacodynamic correlation with DT efficacy and toxicity, and to evaluate inter-cycles AUC stability. For this purpose, blood sampling will be performed at the first and third treatment cycles. For patients still on treatment after Cycle 3, an optional and limited sampling at cycle 4, cycle 6 and beyond (e.g. every 2 cycles until the end of study treatment) will also be performed.

The bioanalytic method will be described in separate bioanalytical study plans and analysis of the study samples will be centrally performed at [REDACTED]. Blood samples collected and stored in the biobank are aimed at measuring total doxorubicin, free doxorubicin and doxorubicinol plasma concentrations. Each sequence of analysis will be performed according to current quality standards, especially in term of quality control samples, calibration curve and acceptance criteria.

Pharmacokinetic data analysis will be performed under the responsibility of the Sponsor. A formal Statistical Analysis Plan (SAP) for PK analysis will provide further details of the statistical analyses and will be finalized before database lock. The section below is an overview of the PK statistical analyses planned for this study.

Total doxorubicin, free doxorubicin and doxorubicinol concentration data will be analysed using a 3 compartment model. This will allow for determination of both the steady-state and the elimination pharmacokinetic parameters of free doxorubicin, total doxorubicin and its major metabolite doxorubicinol.

The following pharmacokinetic parameters will be derived for total doxorubicin, free doxorubicin and doxorubicinol:

C_{max}, T_{max}, AUC (last, and inf), Half-life, Clearance

The study protocol is planned to present pharmacokinetic parameters as mean, standard deviation (SD), coefficient of variation (CV%), median, minimum and maximum values (and geometric mean when appropriate).

The influence of covariates such as demographics and liver impairment will be investigated.

Amount of blood samples taken for the pharmacokinetic study (see appendix VIII)

A maximum of thirty-six (36) blood samples will be taken for PK during the study within the first 3 months. The amount of blood taken each time will be less than 10 ml each: fourteen (14) times during treatment period Day 0 to Day 3, during the 1st and the 3rd Cycle of treatment to measure the study drug concentration in the blood and, if possible, one additional blood sample at Day 4, Day 8, Day 14 and Day 28 of the 1st and the 3rd Cycle.

In patients still on study treatment after Cycle 3, an optional and limited blood sampling will be drawn on each Day 1 (4 times: at T0, 4h, 6h, 8h), Day 14 (once) and Day 28 (once) of Cycle 4, Cycle 6, and beyond (e.g. every 2 cycles until the end of study treatment).

Thus, total amount of blood to be drawn during the study period will not exceed 360 ml throughout the first 3 months (a blood donor usually donates about 500 ml at once). The amount of each additional and optional limited sampling after 3 months for the ongoing patients will not exceed 60 ml every 2 months.

7.3.2. Pharmacogenetic study

The pharmacogenetic study will be realized in all patients who have accepted and signed an appropriate genetic informed consent form.

A blood sample bank will be constituted to evaluate any other potential biomarkers which will be identified as possibly relevant predictive / prognostic factors.

One additional blood sample will be taken for the pharmacogenetic study. The amount of blood is around 10 ml. Measurement of plasma concentrations of biomarkers will be realized before treatment (at baseline).

Analysis will be centrally performed under the responsibility of sponsor (see Annex VIII).

7.4 Supporting board: Independent Data and Safety Monitoring Board

An independent Data and Safety Monitoring Board (DSMB) will be organized to regularly evaluate the safety of DT during the study. The complete role and responsibilities of DSMB is described in the DSMB charter. The DSMB will be provided with blinded safety data by patient and treatment group every 75 patients (around 25 patients/group) and will review the data at least twice a year. The DSMB will remain blinded for its evaluation, but may ask for unblinding if required.

At the end of each meeting, the DSMB will have to make recommendations to the Sponsor as follows:

- To continue the trial without modification;
- To continue the trial and amend the protocol, as specified;
- To suspend the trial pending further information or evaluations;
- To terminate the trial prematurely.

The DSMB will receive every SAE within 24 hours of the knowledge of the occurrence or at the latest, on the following working day.

In case of suspected pulmonary SAEs, DSMB will recommend whether to continue, suspend or definitively stop the recruitment and infusions in the respective cohort and make recommendations to the sponsor.

If deemed necessary, the DSMB may elect to postpone the recommendation, pending external consultation(s) with required specialists and/or receipt of additional data and a subsequent closed DSMB meeting session.

The DSMB members will be appointed by the Sponsor. DSMB is an independent expert group consisting of specialists in hepatology, liver oncology disease, lung diseases and statistics, well experienced in the management of patients with HCC and adverse lung reactions. DSMB will elect the chairman. Appropriate Onxeo (formerly known as BioAlliance Pharma) employees (including Pharmacovigilance and Clinical Departments) will participate to the DSMB meetings but will not have any voting rights.

DSMB will have the responsibility for providing the following:

- Assurance of patient safety,
- Trial integrity,
- Discussion with the Sponsor and required specialists,
- Recommendations and commitment in the study.

Following their risk evaluation, the DSMB reserves the possibility of alerting the Sponsor in the event of observation of highly unexpected events. The DSMB may request a futility analysis on the primary criterion of overall survival. This futility analysis serves one objective: to recommend the potential discontinuation when it is unlikely, based on the interim results, to achieve statistically significant results at the end of the study. This futility analysis will be realized under the responsibility of the DSMB statistician. The results of this futility analysis will be disclosed only to DSMB members. No one in the Sponsor representatives has access to

such information. No information about these results will be communicated to investigators and the International Coordinating Investigator.

Copies of correspondence between the sponsor and DSMB members will be distributed to all DSMB members.

National Authorities as applicable and all investigational centres will be informed of the DSMB recommendations.

7.5 Possible risks or discomforts

Like with any other medicines in cancer treatment, side-effects may occur during the treatment period.

The following side-effects were reported in previous studies: leukopenia, neutropenia, lymphopenia, abdominal pain, thrombopenia, elevated liver enzymes, nausea, anaemia, headache, moderate fever, asthenia, hypotension, cough, diarrhoea, O₂ desaturation, tachycardia, pain, minor dyspnoea, alopecia, vomiting, moderate dorsal, lumbar or chest pains.

The progression of all of these side-effects was favourable more or less rapidly, either spontaneously or after symptomatic treatment. The complete list of TEAE is given in the Investigator's Brochure.

Some serious respiratory disorders have also occurred consisting mainly of decrease in SaO₂, pleural effusion and for the worst cases pulmonary oedema, acute respiratory distress syndrome (ARDS), and death.

Pulmonary adverse events will be collected on a specific adverse event form in the e-CRF.

7.6 Safety measures

In case of unexpected life-threatening AE that may or may not be related to the investigational product, all clinical measures considered as mandatory should be taken and symptomatic treatments administered.

Dose adjustment and dose delay are described in section 6.6. Dose adjustment will be based upon haematologic and non haematologic toxicities observed after the previous dose administration. Any patient who requires a dose reduction will be treated with a reduced dose for any subsequent doses. Arm A patients requiring dose reductions below dose level -1 must discontinue and arm B patients requiring dose reductions below dose level -2 must discontinue.

7.6.1 Pulmonary toxicity

In previous studies where DT was injected through the hepatic intra arterial route in 15-30 minutes, 5 cases of ARDS were reported in 5 patients, resulting in death in two of them. Preclinical experiments showed that respiratory events were prevented by reduction of the DT infusion rate. A careful review of human safety data confirmed that dose and infusion rates were parameters driving the DT toxicity and led to recommend to infuse DT through the IV route over 6 hours. In order to prevent the occurrence of ARDS, respiratory safety measures have been implemented, including premedication with methylprednisolone 32 mg p.o (or equivalent) + non sedating antihistamine H₁ at double dose (e.g. cetirizine 20 mg p.o or equivalent) administered the day and 1 hour before infusion, then the day after infusion, and close monitoring following each infusion:

SaO₂ monitoring during the 6-hour infusion:

- Continuous monitoring of SaO₂:
 - In case of SaO₂ decrease to < 93%, the DT infusion rate will be reduced by half (12-hour infusion). The total dose will not be changed;
 - In case of SaO₂ decrease to ≤ 90%, DT infusion will be **immediately and definitively** stopped;
- Monitoring of respiratory symptoms:
 - In case of a respiratory symptom (dyspnoea, increase in respiratory rate by 5 beats/min and RR > 20/min), the DT infusion rate will be reduced by half (12-hour infusion); the total dose will not be changed;
 - In case of persistence of symptoms in the following hour, DT infusion will be **immediately and definitively** stopped.

SaO₂ monitoring after the end of DT infusion :

A SaO₂ monitoring during 24 hours after infusion start is mandatory.

In case of a marked decrease in SaO₂ or occurrence of respiratory symptoms, the patient will be transferred to intensive care unit for monitoring and treatment until recovery.

In case of SaO₂ decrease (≤ 90%) during or after DT infusion, SaO₂ will be closely monitored and collected every hour until resolution to SaO₂ ≥ 93%.

Patient with a respiratory adverse event during a DT infusion who remain eligible to continue DT treatment will have reinforced respiratory safety measures for each additional DT infusions and SaO₂ collected every hour during infusion and within the 6 hours after the end of infusion.

The recommended treatment of drug-induced pneumonitis is based on systemic corticosteroids with methylprednisolone 1 g/day for 3 days in patients with respiratory failure or lower doses of corticosteroids (i.e methylprednisolone 60 mg every 6 hours) in less severe cases. Before initiating corticosteroid therapy, an infectious etiology must be excluded. Supportive care, bronchodilators, IV fluid, vasopressors, and mechanical ventilation could be indicated in patients with severe hypersensitivity reactions and circulatory collapse (Vahid B., 2008^[49]).

In case of ARDS and/or any related life-threatening respiratory serious adverse event, DT will be definitively stopped and the patient will not receive any additional DT infusion.

In case of grade 3 or grade 4 AE, infusion should be delayed up to 4 weeks, when AE decreases to grade ≤ 2. Further DT infusions should be performed only if adequate respiratory function defined as SaO₂ ≥ 95% is obtained (see section 6.6).

A decrease of SaO₂ below 90%, regardless of any respiratory symptoms or signs, will be considered as SAE and reported to Onxeo (formerly known as BioAlliance Pharma) within 24 hours.

In any case, the total DT dose administered will be carefully recorded in the source document and e-CRF.

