
Safety measures:
 
For patients randomised in the DT groups:
 
Premedication will be administered during three consecutive days starting one day before DT administration. It will consist of methylprednisolone 32 mg (or equivalent) + cetirizine 20 mg (or equivalent) per day.
 
SaO₂ will be monitored during 24 hours as follows:
 
 ○ During the 6-hour DT infusion 
 - Continuous monitoring of SaO₂: 
 ▪ If SaO₂ < 93% → reduction of DT infusion rate by half. No changes in dose; ▪ If SaO₂ ≤ 90% → immediate and definitive infusion stop; - Monitoring of respiratory symptoms: 
 ▪ In case of a respiratory symptom (dyspnoea, increase in respiratory rate by 5 beats/min and RR > 20/min) → reduction of DT infusion rate by half. No changes in dose; ▪ In case of persistence of symptoms within 1 hour → immediate and definitive infusion stop. ○ After the end of DT infusion. 
 - In case of marked decrease in SaO₂ or occurrence of respiratory symptoms, the patient should be transferred to intensive care unit for monitoring and treatment up to recovery. 
In case of SaO₂ decrease (≤ 90%) during or after DT infusion, SaO₂ will be closely monitored and collected every hour until resolution to SaO₂ ≥ 93%.
 
Patients with a respiratory adverse event during a previous DT infusion who remain eligible to continue DT treatment will have reinforced respiratory safety measures for each additional DT infusions and SaO₂ collected every hour during infusion and within the 6 hours after the end of infusion.
 
The recommended treatment of drug-induced pneumonitis is based on systemic corticosteroids with methylprednisolone 1 g/day for 3 days in patients with respiratory failure or lower doses of corticosteroids (i.e
		

NAME OF COMPANY: Onxeo (formerly known as BioAlliance Pharma)	NAME OF FINISHED PRODUCT: Doxorubicin Transdrug™ 10 mg	NAME OF ACTIVE INGREDIENT: Doxorubicin

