
methylprednisolone 60 mg every 6 hours) in less severe cases. Before initiating corticosteroid therapy, an infectious etiology must be excluded. Supportive care, bronchodilators, IV fluid, vasopressors, and mechanical ventilation could be indicated in patients with severe hypersensitivity reactions and circulatory collapse.
 
In case of ARDS and/or any related life-threatening respiratory serious adverse event, DT study therapy will be definitively stopped (i.e. patient will not receive any additional DT infusion).
 
Before each additional DT infusions, the following criteria must be met:
 
- Adequate liver function :
▪ Child-Pugh score from A5 to B7 included (if cirrhosis)▪ Serum bilirubin < 35 µM/L (or 2.0 mg/dL)- Adequate respiratory function defined as SaO₂ ≥ 95%;- Absence of ongoing infection- Adequate haematologic tests :
▪ Neutrophil count ≥ 1000 /mm³▪ Platelets count ≥ 50,000 /mm³▪ Haemoglobin ≥ 10 g/dL- No clinical evidence of upper gastrointestinal bleeding- No other limiting toxicity > grade 2 
In case of grade 3-4 AE, infusion should be delayed up to 4 weeks until resolution or recovery to CTC grade ≤ 2.
 
For patients randomised in the BSC group
 
For patients enrolled in the BSC group, safety measure will be done according to the specificity of the Standard of Care and the local practice.
		

[REDACTED]

LIST OF ABBREVIATIONS AND DEFINITION OF TERMS

AASLD	American Association for Study of Liver Diseases
AE	Adverse Event
AFP	Alpha foetoprotein
ALD	Alcoholic Liver Diseases
ALP	Alkaline Phosphatase
ALT	SGPT or GPT, Alanine Transaminase
AML	Acute Myeloide Leukemia
ARDS	Acute Respiratory Distress Syndrom
AST	SGOT or GOT, Aspartate Transaminase
AUC	Area Under the Curve
BCLC	Barcelona Clinic Liver Cancer
BP	Blood Pressure
BSA	Body Surface Area
BSC	Best Standard of Care
BW	Body Weight
°C	Celsius degree
CBC	Complete Blood Counts
CHF	Congestive Heart Failure
CI	Confidence Interval
Cl	Clearance
CLD	Chronic Liver Disease
CLIP	Cancer of the Liver Italian Program
CK	Creatinin Protein Kinase
CR	Complete Response
CRA	Clinical Research Assistant
e-CRF	Electronic Case Report Form
CRP	C-Reactive Protein
CT	Computed Tomography
CTC	Common Toxicity Criteria
CT scan	Computed tomography Scanner
CV	Coefficient of Variation
D	Day
DCR	Disease Control Rate
DLCO	Carbon Monoxide Diffusing Capacity
DLT	Dose Limiting Toxicity

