6.3 DT Administration

In DT groups, based on DSMB recommendation after their careful review of the safety profile reported in the first 75 patients, a shorter period of hospitalization could be recommended since

version 5.0, June 10th, 2014 as compared to the previous protocol version. The premedication will be unchanged as compared to the previous protocol version and administered to the patient according to each centre's usual practice. On D0, one day before each DT administration, patient will be hospitalized or will have an outpatient visit to check eligibility criteria for continuing treatment and to ensure that the premedication is taken. Patient will receive DT infusion on D1 and will be hospitalized until D2. Patient could be discharged on D2 or on D3 in the absence of toxicity. Hospitalization until D3 is optional.

Hospitalization or outpatient visit on D0 and prolonged hospitalization until D3 will be adapted according to hospital practice and/or patient preference.

Day 0 defined as one day before the treatment with DT

- Premedication with methylprednisolone 32 mg p.o. (or equivalent) and cetirizine 20 mg p.o.(or equivalent);

Day 1 : Day of therapy with DT

- H-1: premedication with methylprednisolone 32 mg p.o. (or equivalent) and cetirizine 20 mg p.o.(or equivalent);
- Fasting is not needed;
- **H0:** 20 mg/m² or 30 mg/m² of DT will be prepared and infused over 6 hours through intravenous route (Appendix VII).
- Patient will have a continuous SaO₂ monitoring during infusion and the 24 hours after the infusion start.

Any modification in the infusion rate must be recorded in the e-CRF (see section 7.6: safety measures).

Day 2 : The day after the DT therapy:

- Premedication with methylprednisolone 32 mg p.o. (or equivalent) and cetirizine 20 mg p.o.(or equivalent);

D0 = D28

Each Cycle will be repeated every 28 days up to progression or toxicity.

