8.3 Serious Adverse Events

An AE is classed as being "serious" during a clinical trial if it:

- Results in death
- Is life-threatening
- Results in persistent or significant disability or incapacity
- Requires in-patient hospitalisation or prolongation of existing hospitalization
- Is a congenital anomaly, or birth defect
- Is a suspected transmission of an infectious agent
- Is an important medical event (requires medical intervention to prevent outcomes listed above).

Life-threatening: The term "life-threatening" in the definition of "serious" refers to an event in which the patient or the subject was at risk of death at the time of the event. It does not refer to an event, which hypothetically might have caused death if it were more severe.

Hospitalisation: Any event leading to hospitalisation or prolongation of hospitalisation will be considered as serious, unless at least one of the following exceptions is met:

- The admission results in a hospital stay of less than 12 hours
- The admission is pre-planned (i.e., elective or scheduled surgery arranged prior to the start of the study)
- The admission is not associated with an AE (e.g., social hospitalisation for purposes of respite care).

However, it should be noted that invasive treatment during any hospitalisation may fulfill the criteria of medically important and, as such, may be reportable as a SAE depending on clinical investigator's judgment. In addition, where local regulatory authorities specifically require a more stringent definition, the local regulation takes precedent.

Disability: A substantial disruption of a person's ability to conduct normal life functions.

Important Medical Event: Any AE may be considered serious because it may jeopardize the patient and may require intervention to prevent another serious condition. As guidance for determination of important medical events, refer to the WHO Adverse Reaction Terminology "Critical Terms List", these terms either refer to or might be indicative of a serious disease state. Such reported events warrant special attention because of their possible association with a serious disease state and may lead to more decisive action.

Note: previous studies have identified acute respiratory distress syndrome (ARDS) as SAE. In order to prevent the occurrence of ARDS, a decrease of SaO₂ below 90% will be considered as SAE.

Pregnancy :

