Actually the population expected in the ReLive study will be markedly different from the population observed in the DOTAHCC1 study. Patients are expected to be more severe and consequently the median survival time of the control group should be markedly lower. A Korean study conducted on a population closer to the one expected for ReLive study has reported a median survival time of 187 days (Woo H.Y., 2011^[50]). Under an exponential distribution, a median survival time of 187 days would correspond to a 1-year survival rate of 25.8% (2-year survival rate of 6.7%). A French cohort study conducted on 1287 naive patients with HCC reported that only 187 patients were eligible for Sorafenib treatment and 103 received Sorafenib in whom a 1-year survival of 16% was reported (Rosa L., 2011^[27]). Under an exponential distribution, a 1-year survival rate of 16% would correspond to a median survival time of 138 days and to a 2-year survival rate of 2.6%.

Following the publication of the positive RESORCE regorafenib phase 3 study in Child Pugh A patients tolerant and progressing under sorafenib, the SAP was revised in order to handle the potential risk of lack of power. Analysis of efficacy and safety of the pooled DT groups versus BSC group was chosen as primary analysis and a more realistic OS in the control group of 8 months instead of 6.6 months (200 days) and an HR of 0.69 instead of 0.60 were considered. Following the recent data of prospective non interventional studies showing that the Child Pugh status is a strong prognostic factor for OS in patients treated by sorafenib (median OS of 13 months in Child Pugh A patients versus 5 months in Child Pugh B), analysis of efficacy and safety in this homogeneous population of Child Pugh A patients from whom the clinical benefit is expected to be higher has been added. An OS in the control group of 9 months and an HR of 0.68 were considered in this population.

The hierarchical sequential closed test procedure will be used to control the overall type I error rate of 5% to evaluate first the primary endpoint OS in the ITT population, then if statistically significant the primary endpoint OS in the ITT Child Pugh A population and then if statistically significant the main secondary endpoints (PFS and OOR) in the ITT Child Pugh A population.

The following sequence will be followed:

- OS in the overall ITT population
- OS in the ITT Child Pugh A population
- PFS in the ITT Child Pugh A population

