9.5 Safety endpoints

Safety analyses will be descriptive and conducted in the safety population.

Descriptive data will be provided for adverse events, laboratory values (biochemistry and hematology), vital signs (weight, blood pressure), clinical exams (normal/abnormal), and concomitant treatments.

Patients with at least one AE, SAE, severe AE, AE leading to discontinuation, AE leading to dose reduction, and AEs of interest will be summarized. Adverse events will be coded using MedDRA.

Respiratory:

- Incidence and duration of reduction of SaO₂ during DT infusion (in DT arms);
- Incidence and severity of respiratory events;

Cardiac:

- Incidence and severity of cardiovascular events (including BP and HR);
- ECG and LVEF change ;

Overall:

- Incidence and severity of all TEAEs and SAEs according to NCI-CTC v4.0 scale;
- Biological (haematology and biochemistry analyses and particularly AST/ALT, WBC);
- Child Pugh Score deterioration.

Safety endpoints will be individually described per subject number, presenting: emergence, description, body system, preferred term, date and time of onset, date and time of last study

drug administration before AE, time from onset since last study drug administration, frequency, severity and seriousness, relationship to study drug, action taken (corrective treatment, hospitalisation...) required and outcome if any.

The treatment emergent AEs (TEAEs), defined as those events that occurred or worsened after the first drug administration, will be summarized by body system and preferred term. The number of emergent AEs and the number of subjects reporting these emergent AEs will be presented by treatment group and overall.

The same table presentation will be used for serious TEAEs, drug related TEAEs and drug related serious TEAEs.

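### An SaO2 below 90% is an SAE even without symptoms, but continuous SaO2 monitoring is required only in the DT arms, so the DT-versus-BSC safety tables mix drug effect with unequal detection

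*Combined protocol and SAP*

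**What the plan says.** **The SAE rule.** Section 7.6.1 says that SaO2 below 90%, "regardless of any respiratory symptoms or signs, will be considered as SAE", to be reported within 24 hours. Section 8.3 repeats, in the general SAE definition, that a decrease "below 90% will be considered as SAE". Neither place limits the rule to one arm.

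**Monitoring, DT arms.** Section 6.3 requires continuous SaO2 "monitoring during infusion and the 24 hours after the infusion start". Section 7.6.1 adds that "monitoring during 24 hours after infusion start is mandatory". The synopsis (Safety measures) places these rules under the line "For patients randomised in the DT groups".

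**Monitoring, BSC arm.** The synopsis says that "safety measure will be done according to the specificity of the Standard of Care and the local practice". Section 6.4 leaves BSC monitoring to the centre's usual practice. Section 6.5 does not require admission and gives visits on days 1 and 14 of each cycle.

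**The tables.** In section 9.5 only the SaO2-reduction endpoint is limited to the DT arms. The next endpoint, "Incidence and severity of respiratory events", is not, and TEAEs and serious TEAEs are presented by treatment group. Section 9.1.2 says: "Analysis of efficacy and safety of the pooled DT groups versus BSC group was chosen as primary analysis". Section 9.6 adds exploratory safety comparisons of each dose with BSC.

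**The concern.** Seriousness can be met by a monitor reading alone, and only the DT arms are required to have the monitor running. A symptom-free fall in a DT patient during the 24 hours becomes an SAE. The same fall in a BSC patient at home is unlikely to be recorded.

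Lung toxicity is the main known risk of this drug: section 7.6.1 reports 5 ARDS cases, two of them fatal, with the earlier and faster intra-arterial route. The respiratory and SAE comparison with BSC will therefore be read closely. As the tables are specified, a reader could not tell how much of a DT excess reflects the drug and how much reflects closer observation.

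**Working it through.** **1. The plan's own figures.** The only figures the plan gives for serious respiratory events are in section 9.8. The probability of at least one event is 1 − (1 − p)^n. For n = 25 and p = 0.1%, 1%, 5% and 10% this gives 0.0247, 0.2222, 0.7226 and 0.9282, as printed. The other rows and the exact confidence limits also reproduce. No printed number is in dispute; the point is about detection.

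**2. Requirements side by side (visible text).**

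| | DT arms | BSC arm |
|---|---|---|
| SAE rule at SaO2 < 90% | applies | applies (8.3 is not arm-specific) |
| Continuous SaO2, 24 h per cycle | mandatory | not required |
| Admission each cycle | yes (6.3) | only if local practice requires it (6.5) |
| Respiratory and serious TEAE tables | included | included |

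Section 9.8 uses 4 injections on average as an example. Over 4 cycles a DT patient has 4 × 24 = 96 hours of continuous reading. A BSC patient has 4 × 2 = 8 scheduled visits, at which spot readings may or may not be taken.

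**3. Illustration for threshold SAEs.** Let q be the true proportion of patients with a fall below 90%, equal in all arms, so that there is no drug effect. Assume DT detects all of them and BSC detects a fraction f. Both q and f are assumptions. With the planned 260 DT and 130 BSC patients, expected counts are 260q and 130qf, and the spurious excess is q(1 − f).

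| q | f | Expected DT | Expected BSC | Spurious excess (points) |
|---|---|---|---|---|
| 2% | 0 | 5.2 | 0 | 2.0 |
| 2% | 0.5 | 5.2 | 1.3 | 1.0 |
| 5% | 0 | 13 | 0 | 5.0 |
| 5% | 0.25 | 13 | 1.6 | 3.75 |
| 5% | 0.5 | 13 | 3.3 | 2.5 |
| 5% | 1 | 13 | 6.5 | 0 |
| 10% | 0 | 26 | 0 | 10.0 |
| 10% | 0.5 | 26 | 6.5 | 5.0 |

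No test is planned. As a gauge of how readily a difference would appear, the probability of a two-sided Fisher p below 0.05 at q = 5% is 0.91, 0.42 and 0.16 for f = 0, 0.25 and 0.5, and 0.04 with equal detection.

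**4. Illustration for all SAEs.** Assume 35% of patients in each group have an SAE for other reasons, and that an independent proportion p of DT patients gains one through the threshold, with none in BSC. DT incidence is 1 − (1 − 0.35)(1 − p). For p = 2%, 5% and 10% this is 36.3%, 38.3% and 41.5%, a relative risk of 1.04, 1.09 and 1.19. The shift is 1.3 to 6.5 points. The 95% half-width for a difference at 35% is 1.96 × √(0.35 × 0.65 × (1/260 + 1/130)) = 10.0 points. The overall SAE table is therefore moved less than its own imprecision. The respiratory table, where events are rarer, is the more exposed.

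**The case against.** The strongest objection is that these events may be real toxicity. Section 4.2 excludes patients with SaO2 below 95%, and section 6.6.2 requires at least 95% before each new infusion. A reading below 90% is thus a fall of more than 5 points from the level required before dosing. Section 7.5 lists desaturation among reported effects, and section 8.3 ties the SAE rule to prevention of ARDS. This objection stands against any plan to make a table without these events the main one.

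Second, a reader might infer that detection and harm could never be separated afterwards. The documents do not support that. There is a specific pulmonary event form (7.5), hourly SaO2 collection after a fall to 90% or less (7.6.1), and per-subject description with timing, action and outcome (9.5). What remains is that the visible plan does not prespecify the separation, and a split chosen later in an open-label trial would be less credible.

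Third, a reader might extend the point to laboratory grades. Sections 7.6.2 and 7.6.3 tie daily tests to study treatment without limiting them to DT, section 6.5 gives BSC visit days rather than a test schedule, and the visit procedures in 7.2.1 are blacked out. An arm difference in laboratory testing is not shown.

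Fourth, BSC visits may include spot SaO2, which is a screening vital sign for all patients (7.1), and the separate SAP named in 9.1.1 may say more. Spot readings would narrow the gap but would not match 24 continuous hours.

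Last, the consequence is bounded. Safety analyses are descriptive (9.5). The safety rule in 9.6 compares DT 30 with DT 20, which share the same monitoring, on discontinuations and deaths due to adverse drug reactions. No decision rule uses the DT-versus-BSC SAE rate.

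**Conclusion.** The concern holds as a matter of interpretation. On the visible text, the by-group SAE and respiratory tables rest on unequal detection, in the direction of overstating DT harm. The size is unknown: for assumed true incidences of 2% to 10% and BSC detection of none to half, the spurious difference runs from 1 to 10 points. It depends on how often symptom-free falls occur and on what BSC visits measure, and neither can be read from the documents.

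OS is unaffected and the DT 20 versus DT 30 comparison largely so. The documents do not support treating all such events as artefact, because some may be true lung toxicity. The plan should be improved on this point, but no formal test or decision rule is invalidated.

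**What to change.** In section 9.5:

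1. Prespecify a flag for SAEs that qualify as serious only through the SaO2 threshold, with no respiratory symptom or sign and no other seriousness criterion from 8.3.
2. Record as a separate item whether an infusion stop or intensive-care transfer under 7.6.1 followed, so that events acted on clinically remain visible and the flag is unambiguous.
3. Tabulate flagged events by DT dose.
4. Keep the all-event DT-versus-BSC SAE and respiratory tables as primary, and place a supplementary version without flagged events beside them.
5. State the difference in SaO2 monitoring between the arms next to these tables.

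Monitoring, treatment rules and expedited reporting stay unchanged. The cost is one flag with its companion item, which could go on the existing pulmonary event form, and a few tables. The risk is that the supplementary table is read as removing true lung toxicity; a footnote should say that it does not.
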